Appendix A – Contour Diabetes App 2.0 Questionnaire

Obtain a synced blood glucose reading

1. Overall, I was able to successfully sync my blood glucose value on the meter with the App.

1= Strongly Agree

2= Agree

3= Neither Agree nor Disagree

4= Disagree

5= Strongly Disagree

No opinion

2. Overall, I am satisfied with how easily my blood glucose value on the meter syncs with the App.

1= Strongly Agree

2= Agree

3= Neither Agree nor Disagree

4= Disagree

5= Strongly Disagree

No opinion

3. The syncing of my blood glucose value from the meter to the App is reliable.

1= Strongly Agree

2= Agree

3= Neither Agree nor Disagree

4= Disagree

5= Strongly Disagree

No opinion

4. The syncing of my blood glucose value from the meter to the App is accurate.

1= Strongly Agree

2= Agree

3= Neither Agree nor Disagree

4= Disagree

5= Strongly Disagree

No opinion

5. Did you change time zones during the study? Yes or No

6. If Yes, did the App adjust to the time zone change as expected or did you experience any problems? Please comment below.

(open text field)

7. Do you have any comments about syncing of the meter with the App?

(open text field)

Access and interpret glucose displays such as expanded graph and sequential views.

8. Overall, I was able to successfully access glucose displays such as Expanded Graph view and My Readings view in the App.

- 1= Strongly Agree
- 2= Agree
- 3= Neither Agree nor Disagree
- 4= Disagree
- 5= Strongly Disagree
- No opinion

9. Overall, I was able to successfully interpret glucose displays such as Expanded Graph view and My Readings view in the App.

- 1= Strongly Agree
- 2= Agree
- 3= Neither Agree nor Disagree
- 4= Disagree
- 5= Strongly Disagree
- No opinion

10. Accessing the Expanded Graph view was:

- 1= Very Simple
- 2= Simple
- 3= Neither Simple nor Difficult
- 4= Difficult
- 5= Very Difficult
- No opinion

11. Using the Expanded Graph view was:

- 1= Very Simple
- 2= Simple
- 3= Neither Simple nor Difficult
- 4= Difficult
- 5= Very Difficult
- No opinion

12. Expanded Graph View in the App was understandable and easy to interpret.

- 1= Strongly Agree
- 2= Agree
- 3= Neither Agree nor Disagree
- 4= Disagree
- 5= Strongly Disagree
- No opinion

13. Expanded Graph View in the App was helpful for me in managing my diabetes.

1= Strongly Agree

2= Agree

3= Neither Agree nor Disagree

4= Disagree

5= Strongly Disagree

No opinion

14. Accessing the My Readings view was:

1= Very Simple

2= Simple

3= Neither Simple nor Difficult

4= Difficult

5= Very Difficult

No opinion

15. Using the My Readings view was:

1= Very Simple

2= Simple

3= Neither Simple nor Difficult

4= Difficult

5= Very Difficult

No opinion

16. My Readings View in the App was understandable and easy to interpret.

1= Strongly Agree

2= Agree

3= Neither Agree nor Disagree

4= Disagree

5= Strongly Disagree

No opinion

17. My Readings View in the App was helpful for me in managing my diabetes.

1= Strongly Agree

2= Agree

3= Neither Agree nor Disagree

4= Disagree

5= Strongly Disagree

No opinion

18. I was able to successfully access the Edit view in the App.

1= Strongly Agree

2= Agree

3= Neither Agree nor Disagree

4= Disagree

5= Strongly Disagree

No opinion

19. Using the Edit view was:

1= Very Simple

2= Simple

3= Neither Simple nor Difficult

4= Difficult

5= Very Difficult

No opinion

20. I think using the Edit view became easier to use after multiple uses.

1= Strongly Agree

2= Agree

3= Neither Agree nor Disagree

4= Disagree

5= Strongly Disagree

No opinion

21. Using the Meal Marker selection screen was:

1= Very Simple

2= Simple

3= Neither Simple nor Difficult

4= Difficult

5= Very Difficult

No opinion

22. Meal Marking in the App was helpful for me in managing my diabetes.

1= Strongly Agree

2= Agree

3= Neither Agree nor Disagree

4= Disagree

5= Strongly Disagree

No opinion

23. I think Meal Marking became easier to use after multiple uses of the App.

1= Strongly Agree

2= Agree

3= Neither Agree nor Disagree

4= Disagree

5= Strongly Disagree

No opinion

24. I found that Meal Marking in the App was useful and I would be likely to use in the future.

1= Strongly Agree

2= Agree

3= Neither Agree nor Disagree

4= Disagree

5= Strongly Disagree

No opinion

25. I used the Manual Blood Glucose Entry Screen in the App.

Yes or No

If 'No' go to Question 27.

26. Using the Manual Blood Glucose Entry screen was:

1= Very Simple

2= Simple

3= Neither Simple nor Difficult

4= Difficult

5= Very Difficult

No opinion

27. Do you have any comments about the glucose displays, meal marking or using the Edit View in the App?

(open text field)

Clarity Of User Instructions

28. The instructions in the short videos and informational screen shots of the App are understandable.

1= Strongly Agree

2= Agree

3= Neither Agree nor Disagree

4= Disagree

5= Strongly Disagree

No opinion

29. The short videos and informational screen shots were helpful to me in using the App.

1= Strongly Agree

2= Agree

3= Neither Agree nor Disagree

4= Disagree

5= Strongly Disagree

No opinion

30. The Help section found in the App was helpful to me in using the App.

1= Strongly Agree

2= Agree

3= Neither Agree nor Disagree

4= Disagree

5= Strongly Disagree

No opinion

31. Do you have any comments about the instructional materials provided with the system?

(open text field)

Recognition of glucose pattern messages

32. The App notified me of some identified blood glucose patterns.

Yes No

If Yes continue to Question **33**. If No, skip to Question **42**.

33. The information I learned through my blood glucose pattern messages in the App was understandable and I was able to interpret them.

1= Strongly Agree

2= Agree

3= Neither Agree nor Disagree

4= Disagree

5= Strongly Disagree

No opinion

34. The information I learned through my blood glucose pattern messages was useful / helpful for me in managing my diabetes.

1= Strongly Agree

2= Agree

3= Neither Agree nor Disagree

4= Disagree

5= Strongly Disagree

No opinion

35. I found the ability to adjust the frequency of the pattern messages helpful.

1= Strongly Agree

2= Agree

3= Neither Agree nor Disagree

4= Disagree

5= Strongly Disagree

No opinion

36. I think the App showed me too many pattern messages.

1= Strongly Agree

2= Agree

3= Neither Agree nor Disagree

4= Disagree

5= Strongly Disagree

No opinion

37. I think the App showed me just the right number of pattern messages.

1= Strongly Agree

2= Agree

3= Neither Agree nor Disagree

4= Disagree

5= Strongly Disagree

No opinion

38. I was able to successfully access Pattern Manager view in the App..

1= Strongly Agree

2= Agree

3= Neither Agree nor Disagree

4= Disagree

5= Strongly Disagree

No opinion

39. The Pattern Manager view was helpful to me in managing my diabetes.

1= Strongly Agree

2= Agree

3= Neither Agree nor Disagree

4= Disagree

5= Strongly Disagree

No opinion

40. I would be likely to use Pattern Manager in the App in the future.

1= Strongly Agree

2= Agree

3= Neither Agree nor Disagree

4= Disagree

5= Strongly Disagree

No opinion

41. Do you have any comments about the glucose pattern messages or the pattern manager in the App? *(open text field)*

Use of “Smart Reminders”

42. I was able to successfully access and use the “Smart Reminders” feature in the App.

1= Strongly Agree

2= Agree

3= Neither Agree nor Disagree

4= Disagree

5= Strongly Disagree

No opinion

43. Accessing the Smart Reminders feature was:

1= Very Simple

2= Simple

3= Neither Simple nor Difficult

4= Difficult

5= Very Difficult

No opinion

44. Using the Smart Reminders feature was:

1= Very Simple

2= Simple

3= Neither Simple nor Difficult

4= Difficult

5= Very Difficult

No opinion

45. I found Smart Reminders test plans that were helpful to me.

1= Strongly Agree

2= Agree

3= Neither Agree nor Disagree

4= Disagree

5= Strongly Disagree

No opinion

46. I followed the Smart Reminders test plans.

1= Strongly Agree

2= Agree

3= Neither Agree nor Disagree

4= Disagree

5= Strongly Disagree

No opinion

47. Smart Reminders in the App were useful / helpful for me in managing my diabetes.

1= Strongly Agree

2= Agree

3= Neither Agree nor Disagree

4= Disagree

5= Strongly Disagree

No opinion

48. I would be likely to use the Smart Reminders feature in the App in the future.

1= Strongly Agree

2= Agree

3= Neither Agree nor Disagree

4= Disagree

5= Strongly Disagree

No opinion

49. Do you have any comments about the Smart Reminders feature in the App?

(open text field)

Other Questions

50. When using health apps, privacy is a very important concern for me.

1= Strongly Agree

2= Agree

3= Neither Agree nor Disagree

4= Disagree

5= Strongly Disagree

No opinion

51. My blood glucose value appearing on my smart phone is not a privacy concern for me. (For example, someone else viewing my BG results on my smart phone is not a concern for me.)

1= Strongly Agree

2= Agree

3= Neither Agree nor Disagree

4= Disagree

5= Strongly Disagree

No opinion

52. Do you have any comments about privacy when using health apps?

(open text field)

53. This BGM/App System will provide me with a better understanding of my disease.

1= Strongly Agree

2= Agree

3= Neither Agree nor Disagree

4= Disagree

5= Strongly Disagree

No opinion

54. This BGM/App System helped me feel more engaged with my diabetes management program.

1= Strongly Agree

2= Agree

3= Neither Agree nor Disagree

4= Disagree

5= Strongly Disagree

No opinion

55. Using this BGM/App System, I felt more motivated to adhere to my health care provider's therapy and testing recommendations.

1= Strongly Agree

2= Agree

3= Neither Agree nor Disagree

4= Disagree

5= Strongly Disagree

No opinion

56. Using this BGM/App System, I found myself testing more frequently throughout the day.

1= Strongly Agree

2= Agree

3= Neither Agree nor Disagree

4= Disagree

5= Strongly Disagree

No opinion

57. What could make you want to use the Contour Next One system and App more frequently?
Please comment *(open text field)*

58. Is there anything in the Contour Next One system and App which causes you to not want to use the system? Please comment. *(open text field)*

59. Do you have any other comments about the BGMs/ App system?*(open text field)*

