This feature set includes sequential day views (My Readings view), modal day view (Expanded Graph view), glucose pattern detection with notifications, and smart test plans. The glucose pattern notifications provide messages to the user that are informational, not prescriptive, using the paradigm “Information, Motivation, and Behavior (IMB)”. These messages are based on algorithmic recognition of patterns in the users’ glucose results and are intended to help guide the user through a series of educational screens to identify the data which triggered the pattern and explore options for addressing the situation. Smart test plans (also called Smart Reminders) can help remind the user to perform certain tasks to improve the quality of information gathered in relationship to a specific event or circumstance (i.e. preparing for a visit with a healthcare professional or if an individual does not like to test).

In summary, Contour Diabetes App 2.0 which is the investigational mobile application under test in this study contains the following updates to App 1.0:

- Detects an additional 19 patterns to the original two (Critical High and Critical Low)
- Expanded smart testing reminder plans

To optimize the functionality of the system, it is imperative that persons with diabetes provide feedback regarding the effectiveness of the Contour Next One system in routine diabetes management, with a focus on the new features in Contour Diabetes App 2.0. This protocol describes a clinical study where people with diabetes will evaluate the Contour Next One blood glucose monitoring system in conjunction with an investigational Contour Diabetes App 2.0.

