Questionnaire outcome – Subjects will complete a questionnaire at the end of the study at Visit 2 that will assess the usability of the App 2.0 with the meter and their experience using the Contour Diabetes App 2.0 system in their daily diabetes management routine. The App features will be evaluated independently by asking a series of questions about each. The features evaluated may include:

- Obtain a synced blood glucose reading
- Recognize and use “Smart Reminders”
- Access and interpret glucose displays such as Expanded Graph and My Readings views.
- Recognize glucose pattern notifications (as applicable since all subjects may not receive pattern messages)

Goal: For the following features, at least eighty five percent (85%) of potential users should be able to report that they were able to successfully utilize the feature. A rating of 1, 2, or 3 for each feature (1=strongly agree, 2=agree, 3=neither agree nor disagree, 4=disagree, 5=strongly disagree) indicates that the subject was able to successfully utilize the feature. These include:

- Obtain a synced blood glucose reading
- Recognize and use “Smart Reminders”
- Access and interpret glucose displays such as Expanded Graph and My Readings views.

Statements such as 1, 8, 9, and 42 in Appendix A correspond to statements subject to the 85% criterion. These statements are shaded.

Secondary Endpoints

- A change from baseline to completion of:
 - HbA1c
 - Fructosamine
 - Weight
 - BMI
 - Total Daily Insulin (self-reported bolus and basal doses)
- Feature Utilization rates

Safety

The following are to be captured:

- Adverse events
- Severe Hypoglycemic episodes
- Hospitalizations

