10.0 DATA COLLECTION AND MANAGEMENT

A unique number will identify each subject. The unique number will be the only identifying information entered. A master list of subject names, with their subject IDs, will be kept by the Investigator at the study site. The Investigator will retain all signed IC documents.

Study data will be recorded on paper forms that will serve as source documents. These data will be entered by the site staff (or designee) into an Electronic Data Capture (EDC) system provided by Ascensia Diabetes Care. In addition to data collection, the EDC system will be used for data cleaning as well as monitoring operations. Site and sponsor users will be trained on the system prior to the study start at their site, and their access to EDC system will be contingent upon successful completion of training requirements. Study personnel will complete and sign all appropriate source document forms in compliance with Good Clinical Practice (GCP). Source documents (Forms) should be completed legibly, in black or blue ink. If it is necessary to make corrections, a single line should be drawn through the original entry, the new entry written in, and the correction initialed and dated by the individual making the correction.

The original forms will be retained by the Investigator for a minimum of three years.

The Investigator or designee will sign and date an Adverse Event Form for each Adverse Event experienced by any subject.

Data Downloaded from the Cloud

Additionally, apart from the data collected, then entered into EDC, de-identified data collected in the Contour Diabetes App will be uploaded to the Cloud throughout the study into a US server (US site data). At the end of the study the cloud data will be downloaded to an Ascensia Diabetes Care database. This downloaded cloud data will be able to be accessed by Ascensia Diabetes Care engineering group and Ascensia Diabetes Care Global Medical/Clinical Affairs personnel. Summaries of the cloud data will be included in the Final Clinical Study Report and Statistics Reports. The downloaded data will include the following information, all of which are anonymous, de-identified subject data:

- Subject study email address
- Meter serial number
- Meter and manually entered blood glucose readings with associated dates, times and meal markers
- Settings: target ranges, low, high, and critical lows and highs
- Entries such as notes, exercise (type and duration), food

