- Smart Reminders – record of reminders set by the subject
- Record of pattern notifications including pattern type, dates, times, and pattern status indicators.

The following will not be saved and included in the study database: subject emergency contact name, phone number or any other identifying information.

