11.0 STATISTICAL METHODS AND ANALYSIS

An $n = 40$ responses yields approximately a 93.3% chance of “passing” the primary objective criteria if there is an 85% probability that a randomly selected person could perform the critical tasks successfully.

Performance Criteria for subject’s success at utilizing system features:

There is at least an 85% probability that any user would be able to utilize the App features with success. A hypothesis test will be performed to test the hypotheses for each feature individually:

$$H_0 : \Pr\{user\ can\ perform\ a\ given\ basic\ task\ successfully\} < 85\%$$

against:

$$H_1 : \Pr\{user\ can\ perform\ a\ given\ basic\ task\ successfully\} \geq 85\%$$

With $n = 40$ responses, we must observe at least 31 responses with a 1, 2, or 3 score on a critical questionnaire statement (statements 1, 8, 9, and 42 as shown in Appendix A) to reject the null hypothesis, H_0 . This criterion yields the following risk characteristics:

There is approximately a 93.3% chance (power) of obtaining at least 31 “successes” out of $n = 40$ responses IF the actual probability of success is 85%. Conversely, there is approximately a 90% chance of failing to obtain at least 31 successes out of $n = 40$ responses IF the actual probability of success is only about 66.8%.

It is likely that the actual sample size will not be exactly 40, but in fact may be slightly higher or lower. Responses of “no opinion” will not be counted for any hypothesis test. The critical values for hypothesis tests will be adjusted for sample size, to maintain approximately the same power characteristics, i.e., the probability of rejecting the null if the success probability is 85% will be kept to be no greater than 95%.

The results accessing each feature will be evaluated independently. Statements 1, 8, 9, and 42 in Appendix A correspond to the primary endpoint and the 85% criterion.

Cluster Analyses and Other Associated Analyses

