Ordinal-scaled variables from ease of use and diabetes management attitude surveys will be used in a k-means cluster analysis, to assess the possibility of unknown groupings (clusters) of subjects within the study sample. Other variables, such as diabetes type, age, gender, and frequency of blood glucose testing will be used to potentially further characterize the groupings. Inasmuch as there is no a priori expectation for the numbers of clusters, nor is there any expectation or hypotheses that any variables will have associations with clusters, these analyses should be considered exploratory.

A condition of hardware/software failure that cause or contribute to a subject's inability to access or utilize any given feature will be considered an un-evaluable observation. (i.e., will not be included in the numerator/denominator for calculating percentage of user success.)

Frequency distributions of scores will be provided for the other variables, i.e., subjects' ratings on ease of use and subjects' ratings on clarity/utility of user instructions, subjects' opinions about their use of the Contour Diabetes App 2.0 system. Correlation coefficient, and associated 95% two-sided confidence interval, will be computed for laboratory HbA1c versus average glucose. Average glucose will be computed from cloud data.

Histograms for the change in HbA1c, fructosamine, weight, and total daily insulin (as reported by subjects) from visit 1 to visit 2 will be constructed. ANOVA (or equivalent method) will be used to determine whether change in HbA1c, Fructosamine, weight, and total daily insulin are significantly different from zero. P-values less than or equal to 0.05 will be considered significant. Confidence intervals (95%, two-sided) for the average change in HbA1c, fructosamine, weight, and total daily insulin dose will be computed.

Average daily utilization rates for selected App features will be computed, together with 95% (non-simultaneous) confidence intervals. Frequency tables for discrete demographic variables will be constructed. Descriptive statistics, such as mean, standard deviation, median, minimum, maximum will be computed for continuously-valued demographic variables (e.g., subject age).

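### A No at statement 32 does not separate subjects sent no pattern message from subjects who missed one, and no planned table matches the answer to the cloud notification record

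*Combined protocol and SAP*

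**What the plan says.** Section 2.0 lists, among the features that the primary objective evaluates, "Recognize glucose pattern notifications (as applicable since all subjects may not receive pattern messages"). Section 3.0 repeats the item under Primary Endpoints, in a list of features that may be evaluated. Neither section includes it in the 85% goal, and Section 11.0 confines the criterion to four other items: "Statements 1, 8, 9, and 42 in Appendix A correspond to the primary endpoint and the 85% criterion".

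In Appendix A, statement 32 ("The App notified me of some identified blood glucose patterns") is answered Yes or No. Yes leads to statement 33, and No skips to statement 42.

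Section 10.0 includes in the cloud download a "Record of pattern notifications including pattern type, dates, times, and pattern status indicators", together with the study email address. Section 5.1.3 shows that the address format contains the subject ID. On use of these data, Section 10.0 says "Summaries of the cloud data will be included in the Final Clinical Study Report and Statistics Reports". Section 11.0 uses cloud data for average glucose, set against HbA1c. It also plans daily utilization rates for selected features, which Appendix C says come from the cloud. For questionnaire items outside the criterion it says "Frequency distributions of scores will be provided for the other variables".

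**The concern.** The where-applicable qualifier implies a denominator: subjects who were sent at least one message. Statement 32 is the only item on whether a message was noticed, and it records what the subject believes was received. A No may mean that no pattern was triggered or that a message was missed, and no later item tells these apart.

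This matters because the 19 additional patterns come first in the list of App 2.0 updates, and Section 1.0 asks for user feedback "with a focus on the new features in Contour Diabetes App 2.0". A low Yes count could mean few messages or missed messages, and these call for different changes to the App. As planned, the report can say how many subjects recall a message, but not what share of those sent one noticed it.

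**Working it through.** **The plan's own figures.** For n = 40 and a threshold of 31, the exact binomial gives P(X ≥ 31 | p = 0.85) = 0.9328 (stated 93.3%) and P(X < 31 | p = 0.668) = 0.9004 (stated about 90%). Both reproduce. They concern statements 1, 8, 9 and 42, and the plan states no figure for statement 32.

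**Inputs.** n = 40 completers (Sections 3.0 and 5.1.1). The number of Yes answers (Y) and the number of subjects with a recorded notification (R) are not in the documents. All values of Y and R below are assumed.

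**The table that is needed.**

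| | Yes at 32 | No at 32 |
|---|---|---|
| Notification recorded | a | b |
| None recorded | c | d |

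Recognition among recipients is a/(a + b). The planned frequency table gives only the column totals, Y = a + c and n − Y = b + d.

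**Step 1: statement 32 alone.** Suppose every Yes is a recipient (c = 0). Then R can be anything from Y to 40, and the rate lies between Y/40 and 100%.
- Y = 24: 24/40 = 60% to 24/24 = 100%.
- Y = 30: 30/40 = 75% to 100%.
- Y = 36: 36/40 = 90% to 100%.

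**Step 2: add only the total number of recipients**, which a cloud summary might report. With Y = 24 and R = 30, the rate is (24 − c)/30.
- c = 0: 24/30 = 80.0%.
- c = 2: 22/30 = 73.3%.
- c = 4: 20/30 = 66.7%.

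The logical minimum is a = Y + R − n = 24 + 30 − 40 = 14, or 14/30 = 46.7%. It requires all 10 non-recipients to answer Yes while 16 of 30 recipients answer No, so it is a bound and not a likely result.

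**Step 3: match by subject.** If all 24 Yes answers fall among 30 recipients, the rate is 24/30 = 80.0%, with exact (Clopper-Pearson) 95% CI 61.4% to 92.3%.

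**Step 4: sensitivity to the definition of a recipient.** If 3 of the 6 recipients who answered No had messages that were never displayed, the denominator is 30 − 3 = 27 and the rate is 24/27 = 88.9% (70.8% to 97.6%). The match removes the ambiguity about who was sent a message. Whether it gives one clean figure depends on what the status indicators record.

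**The case against.** The strongest reply is that the plan never promised this measure. Section 2.0 frames the objective as self-reported success, and statement 32 is a self-report. Syncing and Smart Reminders are also judged by self-report without a planned cloud match. Section 3.0 says only that the features evaluated may include this one, and the feature is outside the 85% criterion. This stands, and it limits the weight of the point. It does not remove it: Section 2.0 lists the feature without that hedge, and its qualifier ties the feature to subjects who receive messages, whom the questionnaire cannot identify.

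Second, the cloud summaries might report how many subjects had notifications, which would largely separate few messages from missed ones. That is fair, but the content of the summaries is unspecified and no subject-level match is committed. What then remains is mainly Yes answers without a recorded notification, and the documents give no evidence on how common these are.

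Third, recall is supported by printed screen shots, the diary, two telephone calls and the Visit 2 interview (Sections 5.1.4 to 5.1.6). These may reduce wrong No answers, but they do not verify receipt.

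Fourth, the pattern status indicators are undefined, so the record may not distinguish issued from displayed messages. This stands, and the fix has to allow for it.

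A reader might also infer that the answers to statements 33 to 40 are compromised because subjects who answered No skip them. The documents do not support that. Asking about comprehension only of those who noticed a message is proper, the skip is printed in the questionnaire, and labelling the base of those tables is a reporting preference.

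**Conclusion.** The point holds as a low-severity gap in a descriptive analysis. The planned frequency table for statement 32 cannot give recognition among subjects who were sent a message, and no planned analysis links the answer to the notification record that would supply the denominator.

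The size is unknown. The illustrations assume 40 completers and invented counts: 60% to 100% for 24 Yes answers if every Yes is a recipient, or 80.0% (61.4% to 92.3%) if those 24 are among 30 recipients. The number of missed messages could be zero.

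Two stronger readings are tempting. One is that a primary endpoint goes unanalysed or that the trial's pass/fail result is in doubt. The documents do not support it: the criterion rests on statements 1, 8, 9 and 42, and statement 32 falls under the planned frequency tables. The other is that many recipients miss their messages, for which the documents offer no evidence.

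**What to change.** Add one descriptive paragraph to Section 11.0, preferably before data lock:

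1. Define a recipient as a completer with at least one pattern notification recorded in the cloud before Visit 2, linked to the questionnaire by the study email address.
2. Cross-tabulate statement 32 against receipt. Report Yes among recipients with an exact 95% CI, show non-recipients as not applicable, and list any Yes without a recorded notification.
3. If the status indicators distinguish issued from displayed messages, use displayed messages for the denominator. This fits the existing rule that a hardware or software failure contributing to "inability to access or utilize any given feature will be considered an un-evaluable observation". If they do not, report on issued messages and state that a No may reflect non-display or recall error.

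The cost is one paragraph and one merge of data already collected, with no new items, visits, subjects or tests. The downside is that the reported figure may be less favourable, and that a recipient's No still needs the caveat in item 3 wherever display cannot be confirmed. Even with display confirmed, recall error remains possible and should be noted.
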